### 5.3 Full Analysis Set

The full analysis set (FAS) will include all patients who have received at least 1 dose (partial or full) of ARRY-382 or pembrolizumab. The FAS will be used for the summary of demographics, baseline characteristics, patient disposition data, and all efficacy analyses.

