**Table 2: Binomial Probabilities of Dose-Limiting Toxicity in a Cohort of 9 Patients**

K	Binomial Probability		
	Exactly k DLTs	≤ k DLTs	>k DLTs
0	0.0260	0.0260	0.9740
1	0.1171	0.1431	0.8569
2	0.2341	0.3772	0.6228
3	0.2731	0.6503	0.3497
4	0.2048	0.8552	0.1448
5	0.1024	0.9576	0.0424
6	0.0341	0.9917	0.0083
7	0.0073	0.9990	0.0010
8	0.0009	0.9999	0.0001
9	0.0001	1.0000	0.0000

DLT=dose-limiting toxicity; k=number of dose-limiting toxicities

For the Phase 2 PD-1/PD-L1 Inhibitor Refractory cohort, the sample size of approximately 20 patients will be evaluated for initial evidence of activity in this PD-1/PD-L1 refractory population.

For the Phase 2 prOVCA cohort, a Simon’s 2-stage optimal design (Simon 1989) will be used in the MSS/MMR-proficient prOVCA population. The null hypothesis of the true response rate is

15% will be tested at one-sided type I error rate of 10%. The alternative hypothesis is the true response rate is at least 35%. Accrual of patients in Stage 1 will continue until 9 evaluable MSS/MMR-proficient patients have been enrolled, with evaluable defined as having received at least one dose of study drug. The analysis for Stage 1 will not occur until all evaluable patients in Stage 1 have had the opportunity to have at least 2 post-baseline tumor assessments (or have discontinued tumor assessments beforehand). If there are fewer than 2 responders in these 9 patients, enrollment into this cohort of the study will be stopped. Otherwise, 14 additional patients will be accrued during Stage 2, for a total of 23 patients enrolled in this cohort. The null hypothesis will be rejected if 6 or more responses are observed in 23 patients. With this sample size, the actual Type I error is 9.9%, and the power is 80%. If the null hypothesis is true, the expected sample size is 15 patients, and the probability of stopping enrollment into this cohort of the study early is 60%. Patients who are MSI-H/mismatch repair-deficient (dMMR) will not be included in the Simon's 2-stage analyses and the study will ensure that the sample size requirements are met by enrolling the required number of MSS/MMR-proficient pOVCA patients.

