For the Phase 2 PDA cohort, a Simon's 2-stage optimal design ([Simon 1989](#)) will be used in the MSS/MMR-proficient PDA population. The null hypothesis of the true response rate is 4%, versus alternative of 15%. Accrual of patients in Stage 1 will continue until 15 evaluable MSS/MMR-proficient patients have been enrolled, with evaluable defined as having received at least one dose of study drug. The analysis for Stage 1 will not occur until all evaluable patients in Stage 1 have had the opportunity to have at least 2 post-baseline tumor assessments (or have discontinued tumor assessments beforehand). If there are no responders in these 15 patients, enrollment into this cohort of the study will be stopped. Otherwise, 14 additional MSS/MMR-proficient patients will be accrued during Stage 2, for a total of 29 patients enrolled in this cohort. The null hypothesis will be rejected if 3 or more responses are observed in 29 MSS/MMR-proficient patients. With this sample size, the actual Type I error is 9.9%, and the power is 80%. If the null hypothesis is true, the expected sample size is 21 patients, and the probability of stopping enrollment into this cohort of the study early is 54%. PDA patients who are MSI-H/dMMR will not be included in the Simon's 2-stage analyses and the study will ensure that the sample size requirements are met by enrolling the required number of MSS/MMR-proficient PDA patients.

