For reporting conventions, minimum and maximum values will be presented with the same decimal precision as collected in the raw data; mean, median, and quartiles should generally be presented to one more decimal place than the raw data; standard deviation should be displayed to two more decimal places than the raw data. Percentages will be reported to one decimal place. Unless otherwise noted, for all percentages, the number of patients in the analysis set who have an observation will be the denominator.

All analyses will be performed and summarized for Phase 1b and Phase 2 separately. All Phase 1b tables will be presented by the following 4 groups, and the listings will be presented by the first 3 groups:

200 mg ARRY-382 + 2 mg/kg Pembro	400 mg ARRY-382 + 2 mg/kg Pembro	300 mg ARRY-382 + 2 mg/kg Pembro	All Phase 1b Patients
-------------------------------------	-------------------------------------	-------------------------------------	--------------------------

All Phase 2 tables, listings and figures will be presented by the following 3 groups:

PD-1/PD-L1 Inhibitor Refractory	prOVCA	PDA
---------------------------------	--------	-----

Data listings will be created for Phase 1b and Phase 2 separately, and will be sorted by patient identifier, parameter, and the corresponding date of assessment. The listing source will be included in the footer of the listings.

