### 7.5 Efficacy Analysis

Efficacy analyses will be performed using the FAS.

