#### 7.5.1 Objective Response Rate

ORR is defined as the proportion of patients who have achieved a best overall response (BOR) of complete response (CR) or partial response (PR) as determined by Investigator review of radiographic disease assessments per RECIST v1.1. Both confirmed and unconfirmed ORR will be summarized, but the primary analysis will be based on confirmed responses.

The BOR is defined as the best response recorded from the study start date until progression and will be determined programmatically based on the Investigator’s assessment of tumor response at each time point per RECIST v1.1. Only tumor assessments performed before the start of any subsequent anticancer therapies and not later than 30 days after last dose of study drug will be considered in the assessment of best overall response. Clinical deterioration or clinical progression noted on the End of Treatment Disposition eCRF will not be considered as documented disease progression for the purposes of the ORR calculation.

The confirmed BOR for each patient is determined from the sequence of overall timepoint (lesion) responses according to the following rules below:

CR = at least two determinations of CR at least 4 weeks apart before progression, where confirmation required, or one determination of CR prior to progression, where confirmation not required.

PR = at least two determinations of PR or better at least 4 weeks apart before progression (and not qualifying for a CR), where confirmation required, or one determination of PR prior to progression, where confirmation not required.

SD = an assessment of SD or better > 6 weeks after start of treatment (and not qualifying for PD, PR or CR).

PD = progression  $\leq$  9 weeks after start of treatment (and not qualifying for CR, PR, or SD).

NE (Not Evaluable) = all other cases (i.e. not qualifying for confirmed CR or PR and without SD after more than 6 weeks or early progression within the first 9 weeks).

Patients with confirmed best overall response 'Not Evaluable' will be summarized by reason for having unknown status. The following reasons will be used:

- No baseline assessment
- No adequate post-baseline assessment
- All post-baseline assessments have overall response of "NE"
- New anticancer therapy started before first post-baseline assessment
- SD occurred  $\leq$  6 weeks after the start of treatment

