- Progression >9 weeks after the start of treatment (i.e. tumor assessment of PD was >9 weeks after start of treatment and there was no tumor assessment in between)

Special (and rare) cases where BOR is 'Not evaluable' due to both SD occurring  $\leq$  6 weeks after start of treatment and progression > 9 weeks after the start of treatment will be classified as "SD occurred  $\leq$  6 weeks after the start of treatment".

The ORR will be calculated with an exact two-sided 95% CI. The 95% CI will be derived using the Clopper-Pearson exact binomial CI method. In addition, the number and percentage of patients in each BOR category (i.e., CR, PR, stable disease (SD), progressive disease (PD), and Not Evaluable) will be summarized.

A figure for duration of exposure and best overall response (confirmed) will be created.

A waterfall plot will be created to show the best percentage change from the baseline in the sum of longest diameters. Patients with baseline and at least one post-baseline tumor assessment will be included in the waterfall plot.

Individual lesion measurements and overall response assessments per RECIST v1.1 will be listed by patient and assessment date.

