#### **7.5.5 Immune-related Response Rate**

Immune-related RR (irRR) is defined as the proportion of patients who achieve immune-related best overall response (irBOR) of immune-related CR (irCR) or immune-related PR (irPR), as determined by the Investigator per irRC, where irBOR is the best response using irRC recorded from the start of study treatment until the end of treatment.

The confirmed irBOR for each patient is determined from the sequence of overall timepoint (lesion) responses per irRC as summarized in Appendix 6 in the study protocol. The derivation of BOR with confirmation requirement as defined in Section 7.5.1 will be used to determine the

irBOR. In addition, Immune-related PD (irPD) needs to be confirmed by a repeat, consecutive assessment no less than 4 weeks from the first documented date.

The irRR will be calculated along with the two-sided exact Clopper-Pearson 95% CIs. In addition, the number and percentage of patients in each BOR category, i.e., irCR, irPR, immune-related SD (irSD), irPD, and immune-related Unevaluable (irUnevaluable) will be summarized.

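### The primary ORR and the other efficacy estimates for the prOVCA and PDA cohorts are assigned to all treated patients, although the objectives and the Simon test are restricted to MSS/MMR-proficient patients

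*SAP*

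**What the plan says.** **Analysis set.** The FAS in SAP 5.3 is every patient who received at least one dose of either drug, with no condition on MSI or MMR status. The same section adds: "The FAS will be used for the summary of demographics, baseline characteristics, patient disposition data, and all efficacy analyses". SAP 7.5 opens with "Efficacy analyses will be performed using the FAS" and makes no exception by cohort.

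**Estimates that follow from it.** For the primary endpoint, SAP 7.5.1 says "Both confirmed and unconfirmed ORR will be summarized, but the primary analysis will be based on confirmed responses" and "The ORR will be calculated with an exact two-sided 95% CI". SAP 7.5.5 says "The irRR will be calculated along with the two-sided exact Clopper-Pearson 95% CIs". DOR, PFS, OS and irPFS fall under the same opening sentence of 7.5.

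**Displays.** SAP 7.1.7 states "All Phase 2 tables, listings and figures will be presented by the following 3 groups"; the groups are the refractory, prOVCA and PDA cohorts, each taken whole.

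**Objectives and test.** SAP 2.1 words the prOVCA and PDA primary objectives for MSS/MMR-proficient patients, and SAP 2.2 does the same for the further-efficacy objectives. SAP 3.2 says for prOVCA that "Patients who are MSI-H/mismatch repair-deficient (dMMR) will not be included in the Simon's 2-stage analyses". It has the same exclusion for PDA and adds that "the study will ensure that the sample size requirements are met by enrolling the required number of MSS/MMR-proficient PDA patients".

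**The concern.** The primary objective in each cohort is to estimate efficacy in MSS/MMR-proficient disease, so the ORR with its interval is the main deliverable. None of the sets in SAP 5.1 to 5.5 carries that restriction, so any treated MSI-H/dMMR patient enters the reported figure.

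The protocol (Version 4) expects such patients. MSI/MMR status is not an eligibility criterion in 5.2, it is confirmed by retrospective central testing (7.1.5), and 9.3 enrolls extra patients to make up for those found MSI-H/dMMR. They are replaced for the Simon count and then put back into the estimate by the SAP.

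One report would then carry a decision in one population and a primary estimate in another. The rejection cut-offs are small (3 responses in PDA, 6 in prOVCA), so one patient is enough to separate the two. In PDA the likely direction is upward: Protocol 2.1.5 cites 5 responses in 6 MSI-H pancreatic patients on pembrolizumab, against a null rate of 4%.

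**Working it through.** **Inputs (SAP 3.2).** PDA: null 4%, alternative 15%, 15 patients in Stage 1, stop on 0 responders, 29 in total, reject on 3 or more. prOVCA: null 15%, alternative 35%, 9 in Stage 1, stop on fewer than 2 responders, 23 in total, reject on 6 or more. Response rate in MSI-H pancreatic cancer: 5/6 (Protocol 2.1.5). The documents give no MSI-H rate for ovarian cancer and no expected number of MSI-H/dMMR patients. A 40% response rate is used below as an assumption.

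**Step 1: reproduce the plan's figures.** With n1 patients in Stage 1, n2 in Stage 2, stopping at r1 or fewer responders and rejecting at r or more in total, P(reject) is the sum over x > r1 of Bin(x; n1, p) × P(Bin(n2, p) ≥ r − x).

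| Cohort | Type I error (stated) | Power (stated) | Early stop under null (stated) | Expected n under null (stated) |
|---|---|---|---|---|
| PDA | 9.92% (9.9%) | 80.1% (80%) | 54.2% (54%) | 21.4 (21) |
| prOVCA | 9.90% (9.9%) | 80.4% (80%) | 59.9% (60%) | 14.6 (15) |

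All reproduce, so the Simon design itself is sound.

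**Step 2: add one MSI-H/dMMR patient to the FAS.** Intervals are Clopper-Pearson 95%, as in SAP 7.5.1.

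| Cohort | MSS/MMR-proficient result | Simon decision | MSI-H patient | Reported on the FAS |
|---|---|---|---|---|
| PDA | 2/29 = 6.9% (0.8 to 22.8) | not rejected | responds | 3/30 = 10.0% (2.1 to 26.5) |
| PDA | 3/29 = 10.3% (2.2 to 27.4) | rejected | does not respond | 3/30 = 10.0% (2.1 to 26.5) |
| prOVCA | 5/23 = 21.7% (7.5 to 43.7) | not rejected | responds | 6/24 = 25.0% (9.8 to 46.7) |
| prOVCA | 6/23 = 26.1% (10.2 to 48.4) | rejected | does not respond | 6/24 = 25.0% (9.8 to 46.7) |

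In each cohort the same reported figure arises from opposite decisions. The largest shifts are 10.0 − 6.9 = 3.1 points in PDA and 25.0 − 21.7 = 3.3 points in prOVCA. Both FAS intervals still contain the null rate (4% and 15%).

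**Step 3: how often the FAS count would reach the cut-off while the Simon test does not reject.** Assume the null is true and exactly one MSI-H/dMMR patient is treated. The MSS/MMR-proficient count must pass Stage 1 and finish one short of the cut-off, and the MSI-H patient must respond.

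- PDA, pass Stage 1 and finish with exactly 2: Bin(1; 15, 0.04) × Bin(1; 14, 0.04) + Bin(2; 15, 0.04) × Bin(0; 14, 0.04) = 0.3388 × 0.3294 + 0.0988 × 0.5647 = 0.1674.
  - At 40% response: 0.1674 × 0.40 = 6.7%.
  - At 5/6 response: 0.1674 × 5/6 = 14.0%.
- prOVCA, pass Stage 1 and finish with exactly 5: 0.0922 by the same sum over 2 to 5 Stage 1 responders.
  - At 40% response: 0.0922 × 0.40 = 3.7%.
  - Over all possible response rates (0 to 100%): 0 to 9.2%.

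**Step 4: expected bias at the null.** The expected FAS ORR is (N × p0 + m × q)/(N + m), where N is the MSS/MMR-proficient total, p0 the null rate, m the number of MSI-H/dMMR patients and q their response rate. For PDA with m = 1: (29 × 0.04 + 0.40)/30 = 5.2%, or 6.6% with q = 5/6, against a true 4%.

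**The case against.** The strongest reply is that SAP 3.2 already settles the matter. The only hypothesis test of ORR in these cohorts is the Simon test, its population is stated, and a specific rule can be read as overriding the general FAS sentence. What would remain is a missing cross-reference for a descriptive estimate. This stands as far as the decision goes: type I error, power and the stopping rule are protected if 3.2 is followed. It does not reach the estimate. SAP 3.2 speaks of the Simon analyses, whereas 5.3 and 7.5 name the FAS for all efficacy analyses and 7.1.7 provides no other column.

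A second reply is that the text is incomplete. The SAP was written against protocol Version 5 and only Version 4 is available, and redacted exploratory text may summarize MSI-H/dMMR patients separately. Both are fair limits. However, the conflict lies within the SAP, sections 5 and 7.5 are not redacted, and a separate exploratory summary would not take these patients out of the primary ORR.

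Third, a reader might rebuild the right figure from the listings, since responses and disease history are listed by patient. That may be possible, but it does not replace a primary estimate in the stated population.

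Fourth, the effect is small and conditional. This is correct, and the conclusion is sized accordingly.

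Finally, leaving out patients of unknown status could cost power. With two fewer Stage 2 patients and unchanged cut-offs, power falls from 80.1% to 76.9% in PDA and from 80.4% to 75.3% in prOVCA. That loss arises only if accrual stops before the required number of MSS/MMR-proficient patients is reached, which SAP 3.2 does not allow.

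**Conclusion.** The concern holds. Read as written, the SAP reports the primary ORR and interval, and irRR, DOR, PFS, OS and irPFS, for the prOVCA and PDA cohorts in a broader population than the one named in the objectives and used for the Simon decision. Treating this as a point that should be fixed is proportionate. One MSI-H/dMMR patient moves the ORR by about 3 percentage points at most, but that is enough to make the reported figure compatible with either decision.

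The size rests on how many such patients are treated, which the documents do not give, and on their response rate, for which the only documented figure is 5/6 from six pancreatic patients. If none is treated, nothing changes. Restricting on MSI/MMR status is not a post-treatment selection, because it is a tumor characteristic present before the first dose.

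**What to change.** Add to SAP section 5 an MSS/MMR-proficient efficacy set for the prOVCA and PDA cohorts: treated patients whose status is MSS/MMR-proficient by central testing or, failing that, by patient records. Use it in those two cohorts for the Simon decisions, the primary ORR with its interval, and irRR, DOR, PFS, OS and irPFS. Amend 5.3 and 7.5 accordingly, and add the set to the table groups in 7.1.7.

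State the rule for unknown status, which is now missing although Protocol 5.2.1 lets the tissue requirement be waived. Such patients stay outside the set, do not count toward the 23 or 29, and are added in one sensitivity analysis. Keep the FAS for the refractory cohort and as the supportive analysis for the other two.

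The cost is SAP wording, one population flag, one extra table group and one sensitivity analysis, with a denominator that may be slightly smaller than the FAS. It should be done before database lock, so that the denominator of the primary endpoint is not chosen after the data are seen.

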### 5.4 Safety Set

The safety set (SS) includes all patients who receive at least 1 dose (partial or full) of ARRY-382 or pembrolizumab. The SS is the same as the FAS in this study.

Unless otherwise specified, the SS will be the default analysis set used for all safety analyses.

### 5.5 Pharmacokinetic Set

The pharmacokinetic set (PKS) includes all patients from SS who have received any active study treatment (ARRY-382), with at least one post-dose blood draw to determine plasma concentration of ARRY-382 and its metabolites (AR00469099, AR00469100 and AR00470870), and who have no protocol deviations or other circumstances that would exclude them from analysis.

## 6.0 CHANGES FROM THE STUDY PROTOCOL

There are no changes from the statistical analyses described in the study protocol at this time.

## 7.0 STATISTICAL METHODS

### 7.1 Reporting Conventions and Definitions

#### 7.1.1 Study Drug

Study drug is defined as ARRY-382 or pembrolizumab.

#### 7.1.2 Study Treatment

Study treatment is defined as the combination of ARRY-382 + pembrolizumab or single-agent ARRY-382.

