6.0 STUDY TREATMENT AND CONCOMITANT MEDICATIONS

The term “study treatment” is defined as ARRY-382 or pembrolizumab.

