6.3.1 General Guidelines

If assessment of the toxicity can be clearly attributed to ARRY-382 or pembrolizumab, administration of the offending drug should be interrupted and the toxicity should be followed until resolution or return to baseline according to the respective dose modification guidelines described in [Sections 6.3.2](#) and [6.3.3](#). Treatment with the other agent in the combination may continue without alterations.

If attribution of the toxicity cannot be clearly ascribed to either ARRY-382 or pembrolizumab, then both agents should be stopped and the toxicity should be followed until resolution or return to baseline. For patients with melanoma, long-term single-agent treatment with ARRY-382 is not recommended; if pembrolizumab is permanently discontinued for these patients, ARRY-382 may also be discontinued. In special circumstances, if a patient is benefitting from therapy, that patient may continue to receive single-agent ARRY-382 after discussion with the Sponsor.

If the toxicity recurs after a dose reduction, the process outlined above should be followed once again to determine attribution to either study drug or both study drugs.

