6.3.2 ARRY-382

General guidelines for dose modifications of ARRY-382 are provided in [Table 8](#). However, Investigators are to use their judgment when assessing the clinical significance of individual AEs.

Table 8: Recommended Dose Modifications for ARRY-382 Treatment-Related Adverse Events

Severity of Event	Action to be Taken
Grade 0-1	
 • Maintain ARRY-382 dose level and provide treatment to control symptoms, if applicable.
Grade 2	
 • Provide treatment to control symptoms, if applicable. If the symptoms cannot be controlled, withhold ARRY-382 until resolution or return to baseline. Then, resume at the original dose. • In the event of a persistent Grade 2 AE that is not responsive to treatment measures or that prevents the patient from resuming treatment, ARRY-382 treatment may be resumed at the next lower dose level. • In the event of irAEs: 
 ○ At first occurrence, withhold ARRY-382 until resolution or return to baseline. Then, resume treatment with ARRY-382 at the same dose level. ○ At second occurrence, withhold ARRY-382 until resolution or return to baseline. Then resume treatment with ARRY-382 at the next lower dose level. ○ At third occurrence, discontinue ARRY-382.
Grade 3	
 • Withhold ARRY-382 until the AE recovers to resolution, or return to baseline. Then, resume treatment with ARRY-382 at the next lower dose level.^a • In the event of a Grade 3 QTcF prolongation or > 60 msec increase in QTcF interval seen on ≥ 2 ECGs (on at least 2 separate ECGs). 
 ○ At first occurrence, interrupt ARRY-382 until QTcF decreases below 500 msec. Then resume treatment at next lower dose level ○ At second occurrence, discontinue ARRY-382.
Grade 4	
 • Discontinue administration of ARRY-382^b
Dose delay > 21 days due to AEs and not underlying disease progression, concomitant illness, or non-medical issues	
 • Discontinue administration of ARRY-382 (unless it is in the best interest of the patient to continue treatment, as judged by the Investigator)

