### **7.6.2 Concomitant Medications**

Concomitant medications are defined as any medications (excluding study drug and prior anticancer treatments) and significant non-drug therapies (including physical therapy, herbal/natural medications and blood transfusions) administered in the study and recorded in the Prior and Concomitant Medications eCRF.

Concomitant medications will be coded using the latest version of the WHO Drug Reference Listing dictionary available at the time of reporting and will be summarized by ATC (level 2) and PT (level 4). These summaries will include:

1. medications starting on or after the start of study treatment but no later than 30 days after last dose of study treatment, and
2. medications starting prior to the start of study treatment and continuing after the start of study treatment.

All concomitant medications will be listed.

Incomplete dates will be handled as described in [Section 7.1.9.1](#).

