### 7.6.4 Adverse Events

AEs and serious adverse events (SAEs) will be coded by PT and SOC using the latest available MedDRA version.

The severity of an AE will be assessed by the investigator using the NCI CTCAE, Version 4.03. For patients with more than 1 AE within a SOC or PT, only the highest grade will be included in by-severity summaries.

The investigator will also assess whether the AE is suspected to be related to study drug (i.e., a treatment-related AE). For patients with more than 1 AE within a SOC or PT, the highest level of relationship (related is higher than not related) will be included in the by-relationship summaries.

For summaries by SOC and PT, each patient will be counted at most once per SOC and at most once per PT. For summaries by PT, each patient will be counted at most once per PT.

Treatment-emergent AEs (TEAEs) will be defined as:

- Any new event that starts after administration of study drug and  $\leq 30$  days after treatment discontinuation.
- Any event that was ongoing when treatment with study drug started and the severity/grade after treatment was higher than the Baseline value (fluctuations below the Baseline severity/grade are not considered as treatment emergent).
- Any new event that starts  $> 30$  days after treatment discontinuation and is assessed by the Investigator as related to study treatment.

Every effort should be made to obtain start dates for adverse events (AEs). If an AE is missing the start date, and the timing of the start date relative to treatment start is not known, it should be considered as treatment emergent for reporting and analysis purposes.

Unless otherwise stated, only TEAEs will be presented in summary tables. However, all AEs will be presented in listings.

Overall summary of safety table will include numbers and percentages of the following:

- Patients who died on study or within 30 days of last treatment
- Patients with at least 1 TEAE regardless of causality
- Patients with at least 1 treatment related TEAE
- Patients with treatment related TEAEs by worst severity
- Patients with at least 1 treatment-emergent SAE (TESAE)
- Patients with at least 1 treatment-related TESAE
- Patients who discontinued study drug due to a TEAE regardless of causality
- Patients who discontinued study drug due to a treatment-related TEAE
- Patients with a dose reduction due to a TEAE
- Patients with a dose interruption due to a TEAE

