All TEAE summaries will be displayed (frequency counts and percentages) alphabetically by system organ class (SOC) and preferred term (PT) by descending frequency within SOC, if not otherwise noted. Individual summary tables showing the incidence of patients with the following subsets of TEAEs will be generated:

- TEAEs, regardless of causality, by SOC, PT and maximum severity
- TEAEs, regardless of causality, by SOC and PT
- TEAEs, regardless of causality, by PT
- Treatment-related TEAEs with suspected relationship to ARRY-382 by SOC, PT and maximum severity
- Treatment-related TEAEs with suspected relationship to pembrolizumab by SOC, PT and maximum severity
- Treatment-related TEAEs with suspected relationship to ARRY-382 by PT
- Treatment-related TEAEs with suspected relationship to pembrolizumab by PT
- TESAEs, regardless of causality, by SOC, PT and maximum severity
- TESAEs, regardless of causality, by SOC and PT
- TESAEs, regardless of causality, by PT
- TESAEs with suspected relationship to ARRY-382 by SOC, PT and maximum severity
- TESAEs with suspected relationship to pembrolizumab by SOC, PT and maximum severity

- TEAEs, regardless of causality, that led to discontinuation of study drug, by SOC and PT
- Treatment-related TEAEs with suspected relationship to ARRY-382 leading to study drug discontinuation by SOC and PT
- Treatment-related TEAEs with suspected relationship to pembrolizumab leading to study drug discontinuation by SOC and PT
- TEAEs that led to dose reduction in ARRY-382 by SOC and PT
- TEAEs that led to dose interruption /delay of ARRY-382 by SOC and PT
- TEAEs that led to dose interruption /delay of pembrolizumab by SOC and PT
- Non-serious TEAEs, regardless of causality, by SOC and PT
- TEAEs that resulted in death on study or within 30 days of last study treatment by SOC and PT

Separate listings for AEs, serious AEs (SAEs), AEs requiring dose interruption, AEs leading to any study drug discontinuation, and death recorded during the study will be provided.

All AEs and their attributes will be presented in data listings sorted by patient identifier, AE and date of onset of the AE.

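### SAP 7.1.2 leaves pembrolizumab given alone out of study treatment; read literally, this closes the concomitant-medication window and one limb of the fatal-TEAE table early

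*SAP*

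**What the plan says.** The SAP defines two neighbouring terms. Section 7.1.1 reads "Study drug is defined as ARRY-382 or pembrolizumab". Section 7.1.2 reads "Study treatment is defined as the combination of ARRY-382 + pembrolizumab or single-agent ARRY-382". The second names the combination and one of the two single-agent states, but not the other.

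Protocol Version 4, section 6.0, gives one definition: study treatment "is defined as ARRY-382 or pembrolizumab". SAP section 6.0 declares no changes from the statistical analyses in the protocol, so the narrower SAP wording is not explained.

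The protocol allows the state that the SAP omits. When a toxicity is clearly attributed to one drug, section 6.3.1 has that drug interrupted and adds: "Treatment with the other agent in the combination may continue without alterations". Table 8 in section 6.3.2 also contains instructions to stop ARRY-382 specifically, for example "Discontinue administration of ARRY-382".

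Two SAP safety outputs end by reference to study treatment. Section 7.6.2 summarizes newly started concomitant medications if they begin "no later than 30 days after last dose of study treatment". Section 7.6.4 plans a table of "TEAEs that resulted in death on study or within 30 days of last study treatment by SOC and PT".

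**The concern.** A programmer who applies 7.1.2 as written would take the last dose of study treatment to be the last ARRY-382 dose, even if the patient went on receiving pembrolizumab within the trial. The 30-day clock for the two outputs above would then start too soon.

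The patients concerned are those who stopped ARRY-382, often for toxicity, and stayed on pembrolizumab. Their later medications are of interest: protocol section 6.3.3 describes corticosteroids and other immunosuppressants as treatment for immune-related events. Medications newly started in that period could be missing from the summary.

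The SAP also uses different end anchors for closely related outputs. The fatal-TEAE table uses last study treatment, the death row of the overall safety summary uses last treatment, the TEAE definition uses treatment discontinuation, and the response window uses the last dose of study drug. Nothing says whether these are meant to be the same date.

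**Working it through.** The plan gives no figure to reproduce. The check is to find which term anchors each rule, and then to size the gap where 7.1.2 applies.

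**Step 1. Anchors**

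| Rule | SAP section | Anchor | Effect of 7.1.2 read literally |
|---|---|---|---|
| Concomitant medications, end | 7.6.2 | last dose of study treatment | shortened |
| Fatal TEAEs, 30-day limb | 7.6.4 | last study treatment | shortened |
| Fatal TEAEs, on-study limb | 7.6.4 | on study (undefined) | probably keeps deaths during pembrolizumab alone |
| Death row, overall summary | 7.6.4 | on study, or last treatment (both undefined) | unclear |
| TEAE, start | 7.6.4 | study drug | none |
| TEAE, 30-day end | 7.6.4, 7.1.9.6 | treatment discontinuation | ambiguous |
| Safety set | 5.4 | either drug | none |
| Treatment start date | 7.1.5 | study drug | none |
| Response window | 7.5.1 | last dose of study drug | none |

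On the TEAE rows: the first limb of the definition begins "Any new event that starts after administration of study drug and", so either agent opens the window. It closes 30 days after treatment discontinuation, and SAP 7.1.9.6 takes that date from the disposition eCRF page. The SAP does not say which date is meant when ARRY-382 stops first, but it does not derive the date from 7.1.2 either.

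**Step 2. Size where 7.1.2 applies**

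Inputs: the cycle length and pembrolizumab interval are 21 days (protocol sections 4.1 and 6.3); the window is 30 days (SAP 7.6.2 and 7.6.4). Assumption: the last pembrolizumab dose falls k cycles after the last ARRY-382 dose, which is day 0.

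- Literal end of window: day 30.
- End of window if either drug counts: day 21k + 30.
- Shortfall: (21k + 30) − 30 = 21k days, covering days 31 to 21k + 30.

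| k (assumed) | Shortfall, days | Days left out |
|---|---|---|
| 1 | 21 | 31 to 51 |
| 4 | 84 | 31 to 114 |
| 8 | 168 | 31 to 198 |

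For the fatal-TEAE table, consider the 30 days after the last pembrolizumab dose. With k = 1, that dose is on day 21, so 30 − 21 = 9 of those days stay inside the literal limb. With k = 2, it is on day 42, already past day 30, so none do. Deaths in that stretch appear in the table only if *on study* is taken to include follow-up.

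**Step 3. What cannot be computed**

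The documents give no count or rate of patients continuing on pembrolizumab alone, so no number of omitted medications or deaths can be given. If ARRY-382 is only interrupted and later resumed, its last-dose date moves forward and the shortfall shrinks or disappears.

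**The case against.** The strongest reply is that the rest of the SAP plainly counts pembrolizumab, so little follows from one loose sentence. The full analysis set and safety set name either drug, and pembrolizumab-related TEAEs have their own tables. Protocol section 10.5 has AEs recorded until 30 days after the last dose of study drug. All AEs, all concomitant medications and deaths recorded during the study are listed, and OS counts every death up to the analysis cutoff. Medications already under way when treatment began stay in the summary through the second item of 7.6.2. All of this stands, and it limits the harm to summary tables.

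Three stronger readings are tempting, and the documents do not support them:

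- *All on-treatment safety windows are cut short.* The main TEAE window opens on study drug and closes at an eCRF-collected date. That end is unclear when one drug stops first, but no shortening is shown.
- *Deaths during pembrolizumab alone drop out.* The fatal-TEAE table includes deaths on study as an alternative to the 30-day limb. The term is undefined, but on its ordinary meaning a patient still receiving protocol pembrolizumab is on study.
- *SAP 7.1.1 and 7.1.2 contradict each other.* They define two different terms. The conflict is with the protocol's definition of the same term.

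The protocol comparison also has a limit. SAP section 1.0 says the SAP was written from Protocol Version 5, and only Version 4 is available. Version 5 may have changed the definition or the single-agent rules. The mixed anchors within the SAP do not depend on the version.

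**Conclusion.** The point holds, at minor severity. SAP 7.1.2 omits a treatment state that Protocol Version 4 allows and includes in its own definition. Followed literally, the omission ends the concomitant-medication window, and the 30-day limb of the fatal-TEAE table, 30 days after the last ARRY-382 dose. The shortfall is 21 days per cycle of pembrolizumab beyond ARRY-382. The 1-to-8-cycle range is an illustration, not an estimate.

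No efficacy endpoint, hypothesis test or stopping rule depends on it. The conclusion assumes that a programmer would apply 7.1.2 as written and that the relevant Version 4 text was not changed in Version 5.

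**What to change.** 1. Reword SAP 7.1.2 so that study treatment means ARRY-382 and/or pembrolizumab, alone or in combination, after checking the wording against Protocol Version 5.
2. State once, in SAP 7.1, that every 30-day safety window (TEAEs, deaths, fatal TEAEs, concomitant medications) runs from the later of the last ARRY-382 dose and the last pembrolizumab dose.
3. Define *treatment discontinuation* and *last treatment* as discontinuation of both drugs. Say which eCRF date or dosing record supplies that date when one drug stops first.
4. Define *on study* for the death row and the fatal-TEAE table, so that both count deaths over the same period.

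The cost is a few sentences in the SAP. The primary analysis does not change, and no new AE collection is needed. If the narrower definition was intended, SAP section 6.0 should instead declare it as a change and give the reason.
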